1.0 Background

1.1 Treatment

Active cancer is associated with a markedly increased risk of both incident and recurrent venous thromboembolism. The rate of recurrence has been estimated to be between 2 to 9 fold higher compared to patients without cancer (1-8). For those cancer patients who suffer a VTE recurrence, the risk of death is increased 3-fold particularly if the recurrent event is a pulmonary embolism (9). In keeping with these data, current guidelines recommend continued anticoagulation therapy beyond the acute treatment phase of 3 – 6 months until there is no longer evidence of active cancer (10). This recommendation distinguishes primary treatment (first 3 – 6 months following VTE confirmation) from secondary prevention which includes continued treatment beyond 6 months. These guideline recommendations however are based on scant data with an evidence grade limited to expert opinion only (Grade 2C)(10). Of note, patients with cancer also carry an increased risk of anticoagulant associated major bleeding (2, 5, 11-14). Balancing the risk of VTE recurrence with the risk of anticoagulant associated major bleeding complicates decision making for these patients. Prolonged anticoagulant therapy may not be beneficial for all cancer patients and may indeed provoke harm in some. In the end, there are limited data to inform decision making for these patients beyond 6 months of therapy.

The LITE investigators randomized 200 cancer patients to receive warfarin or low molecular weight heparin (tinzaparin) for 3 months for the acute treatment of VTE (15). Thereafter, patients were assessed for an additional 9 months following anticoagulation discontinuation. At three months, 6% of those patients randomized to tinzaparin compared to 10% on warfarin suffered an acute VTE recurrence which did not differ significantly between treatment allocations. At 12 months, an additional 7% of patients in the tinzaparin group (total of 13%) compared to an additional 16% in the warfarin arm (total of 26%) suffered VTE recurrence ($p=0.044$; risk ratio 0.44; absolute difference 9.0%, (95% CI -21.7% to -0.7%)). Major bleeding events were 7% for both groups at 3 months. Death occurred in 20% for both groups at 3 months and 47% of both groups at 12 months. The high rate of VTE recurrence and death can be appreciated following anticoagulation discontinuation.

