3.0 Patient Eligibility

3.1 Inclusion Criteria

3.11 Age \geq 18 years.

3.12 Confirmed acute index (original venous thrombotic) event: lower extremity or upper extremity (jugular, innominate, subclavian, axillary, brachial) DVT, PE, splanchnic (hepatic, portal, splenic, mesenteric, renal, gonadal), or cerebral vein thrombosis for which the patient has received \geq 180 days (but \leq 365 days) of anticoagulant therapy prior to registration. The date, imaging modality, and location of index event will be required. The date of initiation and specific type of anticoagulants used will also be required.

3.13 Active cancer defined as metastatic disease and/or any evidence of cancer on cross-sectional or PET imaging, cancer related surgery, chemotherapy or radiation therapy within the past 6 months. Note: non-melanoma skin cancer does not meet the cancer requirement.

3.14 Life expectancy \geq 6 months.

3.15 ECOG Performance Status (PS) of 0, 1, or 2. (Form is available on the ACCRU web site
[REDACTED]

3.16 The following laboratory values obtained \leq 30 days prior to registration.

- Hemoglobin \geq 8 g/dL
- Platelet count \geq 50,000/mm³
- Alanine aminotransferase (ALT) or Aspartate transaminase (AST) \leq 3 x ULN
- Calculated creatinine clearance must be \geq 30 ml/min using the Cockcroft-Gault formula below:

Cockcroft-Gault Equation:

$$\text{Creatinine clearance for males} = \frac{(140 - \text{age})(\text{weight in kg})}{(72)(\text{serum creatinine in mg/dL})}$$

$$\text{Creatinine clearance for females} = \frac{(140 - \text{age})(\text{weight in kg})}{(72)(\text{serum creatinine in mg/dL})} * (0.85)$$

3.17 Negative serum or urine pregnancy test done \leq 7 days prior to registration, for women of childbearing potential only.
 Note: A woman of childbearing potential (WOCBP) is defined as any female who has experienced menarche and who has not undergone surgical sterilization (hysterectomy or bilateral oophorectomy) and is not postmenopausal. Menopause is defined as 12 months of amenorrhea in a woman over age 45 years in the absence of other biological or physiological causes.

3.18 Ability to provide informed written consent.

3.19 Willing to undergo monthly follow-up assessment, either in person at the enrolling institution or by telephone (script in Appendix V).

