11.0 Treatment Evaluation Using RECIST Guideline – Not applicable

12.0 Descriptive Factors – Not applicable

13.0 Treatment/Follow-up Decision at Evaluation of Patient

13.1 A patient is deemed *ineligible* if after registration, it is determined that at the time of registration, the patient did not satisfy each and every eligibility criteria for study entry. The patient may continue treatment off-protocol at the discretion of the physician as long as there are no safety concerns, and the patient was properly registered. The patient will go off study.

- If the patient received treatment, all data up until the point of confirmation of ineligibility must be submitted.
- If the patient never received treatment, on-study material must be submitted.

13.2 It is deemed a *major violation*, if protocol requirements regarding treatment of the patient in cycle 1 of the initial therapy are severely violated that evaluability for primary end

point is questionable. This determination needs to be made by an investigator blinded to treatment allocation.

- 13.3 It is deemed a *cancel* if the patient is removed from the study for any reason before any study treatment is given. On-Study material and the End of Active Treatment/Cancel Notification Form must be submitted. No further data submission is necessary
- 13.4 If the patient meets criteria for a major bleed, they will have met a major safety endpoint and will be removed from the study. All data up until the point of major bleed should be entered. The patient will then be managed as appropriate per the clinical situation and current guidelines.
- 13.5 If the patient meets criteria for a recurrent venous thromboembolic event, they will have met a major secondary endpoint and will be removed from the study. All data up until the point of a recurrent venous thromboembolic event should be entered. The patient will then be managed as appropriate per the clinical situation and current guidelines.
- 13.6 If the patient suffers a non-major clinically relevant bleeding event, they will have met a major safety endpoint. Medical management will be provided in accordance with the location and severity of the bleeding event. This may include temporary cessation of study medication. Once the bleeding event has been appropriately managed, they will restart study medication and will be followed appropriately per protocol. They will not be removed from the study for this event.

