16.0 Statistical Considerations and Methodology

16.1 Sample Size Determination

The primary objective of this study is to determine whether apixaban 2.5 mg twice daily has less bleeding (major bleeding plus clinically relevant nonmajor bleeding) compared to apixaban 5 mg twice daily for secondary VTE prevention in patients with active cancer, previously confirmed deep-vein thrombosis (DVT) or pulmonary embolism (PE) for which they have completed at least 6 months (but no more than 12 months) of anticoagulant therapy. Important assumptions include both clinical and trial observation that bleeding rates in cancer patients with VTE are higher than non-cancer patients. As such, a recent meta-analysis of cancer patients treated with direct factor inhibitors showed that rates of major bleeding were 3.2% and clinically relevant non-major bleeding 14.5% (19). This would equate to rates of 17.7% for these combined outcomes.

The trial is designed as a two-arm, double-blind, randomized study. Patients will be randomized at a 1:1 ratio to receive either 5 mg or 2.5 mg of apixaban twice daily. Assuming the combined bleeding event rate is 9% in the 2.5 mg arm, and 18% in the 5 mg arm, a sample size of 352 (176 per arm) will give us approximately 70% power to detect a difference between the two arms (using a two-sample comparison of proportions with a two-sided alternative at a 5% significance level). The sample size is inflated by 5% to a total of 370 (185) to account for ineligibility and cancellation. We anticipate accruing 15 patients per month to this trial. Based on this accrual rate, we anticipate the trial will complete accrual in 24 months. With the last patient accrued followed for 12 months, the primary analysis will be conducted approximately 36 months after the trial opening. The sample was calculated using EAST 6.3 (Cytel Inc.).

16.2 Primary Hypothesis:

We hypothesize that apixaban 2.5 mg twice daily is associated with a significantly lower combined rate of major bleed plus clinically relevant nonmajor bleed compared to apixaban 5 mg twice daily for the secondary prevention of VTE in patients with active cancer and confirmed deep-vein thrombosis (DVT) or pulmonary embolism (PE) who have completed at least 6 months (but no more than 12 months) of anticoagulant therapy.

16.21 Primary Safety Analysis:

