All patients who received at least one dose of either apixaban 2.5 mg or apixaban 5 mg will be included in the primary analysis. Patients will be analyzed according to the drug they received because this is a safety analysis rather than an efficacy analysis. The analysis of major bleeding plus clinically relevant nonmajor bleeding events will primarily focus on those events which occurred during treatment or within 7 days of treatment discontinuation. Major bleeding events observed later will be described separately.

It should be noted that this study is powered for our primary analysis, in which the proportion of patients experiencing at least one bleeding event within 12 months of beginning treatment will be compared across the two study arms using a two-sample comparison of proportions with a one-sided alternative at a significance level of 5% (i.e. a “Z” test).

Though **not part of the primary analysis**, a number of additional analyses of the primary endpoint will also be performed to further explore the data. These should be viewed as additional secondary analyses. In particular, frequency of major bleeding and clinically relevant non-major bleeding will be tabulated by treatment arm. Incidence of major bleeding and clinically relevant non-major bleeding will be estimated using the cumulative incidence function with death without major bleeding or clinically relevant non-major bleeding and with adverse events that results in termination of treatment (including vascular events) as competing risks. The time to event is defined as the time from randomization to the first occurrence of a major bleeding, a clinically relevant non-major bleeding, death without major bleeding or clinically relevant non-major bleeding, or an adverse events that results in termination of treatment (including vascular events). Patients who were lost to follow-up, who withdrew informed consent before the end of the predefined study duration will be censored at the last day the patient had a complete assessment for study outcomes within the intended

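### The primary 12-month bleeding proportion counts dosed patients who are lost or withdraw without a bleed as bleed-free for the full 12 months, while the plan's own cumulative-incidence analysis censors them

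*Combined protocol and SAP*

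**What the plan says.** Section 2.11 defines the primary safety endpoint as the proportion of patients with at least one major or clinically relevant non-major bleed within 12 months of beginning treatment. Section 16.21 sets the denominator: "All patients who received at least one dose of either apixaban 2.5 mg or apixaban 5 mg will be included in the primary analysis". Each arm is made up by the drug actually received. The analysis focuses on bleeds during treatment or within 7 days of stopping, and the arms are compared by a one-sided 5% Z test on the two proportions.

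Section 16.21 also plans a cumulative-incidence analysis, which it labels as secondary. There, death without a bleed and adverse events that end treatment (vascular events included) are competing risks. Loss to follow-up and withdrawal of consent have a censoring rule, quoted here without its closing words: such a patient "will be censored at the last day the patient had a complete assessment for study outcomes within the intended". The 12-month difference from that analysis is then to be tested with a binomial normal approximation.

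Section 16.3 is headed as the handling of missing data, but it covers only monitoring, auditing and source checking. Section 16.1 inflates the sample by 5% for ineligibility and cancellation. Section 13.3 defines a cancel as someone removed before any study treatment, so cancellations are not losses after dosing.

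**The concern.** The plan never says in words that an early leaver is scored bleed-free. It follows from three provisions together: the denominator is every dosed patient, the numerator is limited to bleeds observed on treatment or shortly after, and no rule covers incomplete follow-up. A patient who withdraws at month 2 has about 2 months in which a bleed could be counted, yet enters the test as a 12-month non-event.

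Two things are at stake. The figure reported as the 12-month bleeding proportion is too low in both arms. And if loss or withdrawal differs between arms, the arm whose patients leave sooner looks safer for a reason unrelated to dose. The plan already contains an analysis that treats these patients properly, but that analysis does not decide the trial.

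**Working it through.** **Inputs from the documents (16.1, 16.21).** Planned rates: "Assuming the combined bleeding event rate is 9% in the 2.5 mg arm, and 18% in the 5 mg arm". Size and power: "a sample size of 352 (176 per arm) will give us approximately 70% power". Design test: "using a two-sample comparison of proportions with a two-sided alternative at a 5% significance level". The primary analysis in 16.21 is one-sided at 5%.

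**Inputs assumed.** The documents give no rate of loss, withdrawal or death for this trial. I assume constant, independent hazards and show a range.

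**1. The plan's power.** Power = Φ[(|p2 − p1| − z·√(2p̄(1 − p̄)/n)) / √((p1(1 − p1) + p2(1 − p2))/n)], with p1 = 0.09, p2 = 0.18, p̄ = 0.135 and n = 176.
- Two-sided (z = 1.96): (0.09 − 1.96 × 0.03643)/0.03611 = 0.515, so power is 69.7%. The stated 70% reproduces.
- One-sided (z = 1.645): (0.09 − 1.645 × 0.03643)/0.03611 = 0.833, so power is 79.8%.

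Both assume that every patient's 12-month status is known.

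**2. Understatement.** Let L = −ln(1 − 12-month bleeding risk) and M = −ln(1 − 12-month exit risk). The proportion observed to bleed before exit is L/(L + M) × (1 − e^−(L+M)). For 9% and 18%, L = 0.0943 and 0.1985.

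Death without a bleed is a true non-event, so the fair target is the incidence with death competing. With 20% deaths, M = 0.2231:
- 2.5 mg: 0.0943/0.3175 × 0.272 = 8.1%
- 5 mg: 0.1985/0.4216 × 0.344 = 16.2%

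Now add loss or withdrawal, scored as bleed-free. Combined exit is 1 − 0.8 × 0.9 = 28%, or 1 − 0.8 × 0.8 = 36%.

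| Loss or withdrawal | M | 2.5 mg | 5 mg | Difference (points) |
|---|---|---|---|---|
| none (target) | 0.2231 | 8.1% | 16.2% | 8.1 |
| 10% | 0.3285 | 7.7% | 15.4% | 7.7 |
| 20% | 0.4463 | 7.3% | 14.6% | 7.3 |

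**3. False difference.** Take a true risk of 18% in both arms, no deaths, and unequal exit. The one-sided rejection rate is 1 − Φ[(1.645·SE0 − d)/SE1], where d is the 5 mg minus the 2.5 mg crude proportion, SE0 is the pooled standard error and SE1 the unpooled one.
- Exit 20% on 2.5 mg, 10% on 5 mg: 16.2% vs 17.1%, d = 0.0092; (0.0653 − 0.0092)/0.0397 = 1.41, so the error is 7.9%.
- Exit 40% vs 20%: 14.2% vs 16.2%, d = 0.0198; (0.0630 − 0.0198)/0.0383 = 1.13, so the error is 13.0%.
- Imbalance reversed: the error falls to 3.0% and 1.5%.
- With 20% deaths added in each arm (combined exit 36% vs 28%, then 52% vs 36%): 14.6% vs 15.4% and 12.9% vs 14.6%, with errors of 7.6% and 12.0%.

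**4. Power under either estimator.** True rates 9% vs 18%, equal exit, no deaths, two-sided 5%. The crude proportion uses an unpooled Z. The censored estimator uses the Greenwood variance (1 − p)² × L/(L + M) × (e^(L+M) − 1)/n, where p is the 12-month bleeding risk.

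| Exit | Crude | Censored |
|---|---|---|
| 20% | 65.1% | 65.2% |
| 30% | 62.2% | 62.1% |
| 40% | 58.9% | 58.5% |

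The two agree to within half a point. On the one-sided test of 16.21, the crude proportion keeps about 76%, 73% and 70%.

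**The case against.** The strongest reply is that an all-treated, on-treatment-plus-7-days proportion is a deliberate choice, which 16.21 explains as suited to a safety analysis. Some attrition is limited by design: section 13.7 keeps patients on drug through disease progression and hospice, and section 8.2 lets held patients resume. Cumulative-incidence, intent-to-treat, 6-month and Cox analyses are also planned. All of this is true, but none of it says how a lost or withdrawn patient is scored in the deciding test.

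A reader might infer more than the documents support:

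- **That all early exits are mis-scored.** The entry criterion "Life expectancy \geq 6 months" and the cited earlier trial, where "Death occurred in 20% for both groups at 3 months and 47% of both groups at 12 months", both concern death, which both estimators count as no bleed. They do not support a high rate of loss or withdrawal.
- **That patients removed for recurrent VTE are handled inconsistently.** Section 13.5 says "All data up until the point of a recurrent venous thromboembolic event should be entered", so later bleeds are unseen. But the planned cumulative incidence makes vascular events that end treatment a competing risk. On the natural reading both analyses treat these patients alike. Censoring them instead would be a new and debatable estimand.
- **That a less protective dose gains on safety.** This needs a dose difference in recurrence. Section 1.4 cites 1.7% on both doses, although mostly in patients without cancer.
- **That the scoring costs power.** Step 4 shows that it does not. The loss comes from shorter observation, and changing the estimator does not recover it.
- **That the crude figure cannot match the planning rates.** Section 16.1 takes 17.7% from a meta-analysis without saying whether it is a crude proportion. If it is, the design rate already contains some attrition.

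**Conclusion.** The point holds for loss and withdrawal. Followed as written, the primary test counts these patients as 12-month non-events, and the plan's secondary analysis contradicts that treatment. With 10% to 20% loss or withdrawal on top of 20% deaths, the understatement is about 0.4 to 0.8 points on 2.5 mg and 0.8 to 1.6 points on 5 mg. A false difference arises only if exit is unequal: a 10-point imbalance moves the one-sided error from 5% to about 8%, and a 20-point imbalance to about 13%. It moves below 5% if the imbalance runs the other way. Nothing in the documents tells us which arm would lose more patients, and double-blinding makes a large imbalance less likely.

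These sizes rest on constant independent hazards and on exit rates that I assumed. This is an inexpensive improvement to the primary analysis. It does not show that the trial is underpowered or that the safety population is wrong.

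**What to change.** In 16.21, make the already planned 12-month cumulative incidence of major plus clinically relevant non-major bleeding the primary comparison:
- Censor lost and withdrawn patients at their last complete assessment.
- Keep death and adverse-event termination, vascular events included, as competing events as already specified.
- Test the difference with that estimator's own standard error instead of the binomial approximation now written.
- State one time origin, since the proportion runs from the start of treatment and the cumulative incidence from randomization. Say also that the 7-day window applies.

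Keep the crude proportion as a supportive analysis. Add a sensitivity analysis that censors patients who stop drug early for other non-bleeding reasons, including recurrent VTE. Report time on drug and reasons for stopping by arm. Put the scoring rule for incomplete follow-up in 16.3, and carry it through to the intent-to-treat and 6-month analyses in 16.22.

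The cost is protocol and SAP wording, as the estimator is planned and the data are collected. The downsides are a slightly wider standard error and the assumption that loss and withdrawal are unrelated to bleeding risk, which is why the crude result should stay beside it.

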1.5 General Design

This is a multicenter, randomized, double blind, superiority trial for safety. Participating centers will be from the Academic and Community Cancer Research United (ACCRU) research consortium. This research consortium is comprised of more than 80 leading academic institutions and community oncology practices in the United States and Canada. The goal of this consortium is to collaborate with industry partners to develop and conduct clinical trials in cancer research.

Subjects will be screened at both outpatient clinic visit appointments and during hospitalizations using direct referrals or by daily automated screening of the electronic medical record. Interested qualified subjects will be consented and offered participation in this trial. Subjects will be considered for trial participation if they have evidence of active cancer and have a history of a documented venous thrombotic event for which they have received at least 6 months (but not more than 12 months) of anticoagulant therapy. Both the date and location of the original thrombosis will be recorded, as well as the anticoagulant used for the original treatment. After randomization, patients will be allocated to receive either apixaban 5 mg twice daily or 2.5 mg twice daily. Allocation to treatment will be done centrally. Once consent has been obtained, baseline laboratory values will be established and subjects will begin treatment and follow-up for 12 months.

The principal safety outcome will be a combined endpoint of major bleeding plus clinically relevant non-major bleeding. All episodes of major bleeding, clinically relevant non-major bleeding and deaths will be evaluated by a central, blinded, independent adjudication committee. Adjudication results will be the basis for the final analyses. An independent data and safety monitoring board (DSMB) will monitor the patients’ safety and give recommendations to the executive committee.

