6.2 Randomization Procedures

- 6.21 The factors defined in Section 5.0, together with the registering membership, will be used as stratification factors.
- 6.22 After the patient has been registered into the study, the values of the stratification factors will be recorded, and the patient will be assigned to one of the following treatment groups using the Pocock and Simon dynamic allocation procedure which balances the marginal distributions of the stratification factors between the treatment groups (Pocock-Simon).
 - Apixaban 2.5 mg twice daily.
 - Apixaban 5 mg twice daily.

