study period. The incidence curves of major bleeding and clinically relevant non-major bleeding will be plotted. The incidence of major bleeding and clinically relevant non-major bleeding will be summarized as a combined endpoint and separate endpoints by treatment arm. The difference in the incidences of the combined endpoint at 6 months and at 12 months between treatment arms will be estimated and tested using a normal approximation of the binomial distribution. All tests will be conducted at the one-sided 0.05 significance level.

The incidences of death due to cancer or other causes (without major bleeding or clinically relevant non-major bleeding) and adverse events that result in termination of treatment will be estimated and compared using the same approach.

A sensitivity analysis for these endpoints will be conducted using a stratified (by stratification factors listed in Section 5.0) Cox model adjusting for baseline covariates including location of DVT, renal clearance, age, sex, mobility at randomization, pulmonary disease, and cardiac disease.

16.22 Secondary Safety Analysis:

A secondary safety analysis of the primary safety endpoint will be performed on an intent-to-treat basis using the same approach described in Section 16.21. In addition, we will compare proportion of patients who experience at least one bleeding event (i.e. the primary endpoint) within 6 months of beginning treatment across the two study arms. As with the primary analysis, this will be done using a two-sample comparison of proportions with a one-sided alternative at a significance level of 5%.

16.23 Secondary Efficacy Analysis:

For the secondary efficacy analysis, the time to the first event of the composite DVT/PE outcome will be analyzed using the same method described in Section 16.21. For this outcome, death without DVT/PE and adverse events leading to termination of treatment will be treated as the competing risks.

16.3 Handling of Missing Data:

Monitoring and auditing procedures should be followed, in order to comply with Good Clinical Practice (GCP) guidelines. Each center will be audited at regular intervals to ensure compliance with the protocol, GCP and legal aspects. This will include on-site checking of the CRF for completeness and clarity, cross-checking with source documents, and clarification of administrative matters.

16.4 Interim Analysis and Study Monitoring:

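### The primary and six-month tests omit the minimisation factors (valid, slightly conservative), and the cumulative-incidence tests, read literally, use a binomial variance despite censoring

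*Combined protocol and SAP*

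**What the plan says.** **Allocation.** Section 5.0 lists three two-level factors: cancer stage, Khorana risk and location of the initial thrombosis. Section 6.21 says these, "together with the registering membership, will be used as stratification factors". Section 6.22 uses Pocock-Simon dynamic allocation, which "balances the marginal distributions of the stratification factors between the treatment groups". Section 1.5 describes the consortium as "comprised of more than 80 leading academic institutions and community oncology practices".

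**Primary and six-month tests.** Section 16.21 has the 12-month proportions "compared across the two study arms using a two-sample comparison of proportions with a one-sided alternative at a significance level of 5" percent and calls this a Z test. For six months, 16.22 says: "As with the primary analysis, this will be done using a two-sample comparison of proportions". Neither test has strata or covariates.

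**Secondary incidence analyses.** Section 16.21 also plans a cumulative incidence function with competing risks. Patients who are lost or withdraw "will be censored at the last day the patient had a complete assessment for study outcomes". The 6- and 12-month differences between arms are then "estimated and tested using a normal approximation of the binomial distribution". The same approach is carried to death and treatment-ending adverse events (16.21), the intent-to-treat analysis (16.22) and the DVT/PE analysis (16.23).

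**Where the factors do appear.** "A sensitivity analysis for these endpoints will be conducted using a stratified (by stratification factors listed in Section 5.0) Cox model". Registering membership is not in Section 5.0, so it is not a stratum there.

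**The concern.** There are two separate, small points.

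1. Minimisation forces the arms to be alike on the chosen factors. If those factors predict bleeding, the true variance of the difference in proportions is smaller than the unstratified formula assumes. The Z-test then rejects less often than its nominal 5% and gives away some power. In a trial planned at about 70% power, a gain that needs no patients is worth considering.

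2. A binomial variance with every patient in the denominator treats everyone as followed to the time point. A cumulative incidence estimated with censoring carries less information than that. The standard error is then too small, and the one-sided tests reject too often under the null.

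**Working it through.** **Inputs from the documents.** 9% against 18%, 176 per arm (352 in total), 1:1 allocation (16.1); one-sided 5% Z-test (16.21); minimisation on three binary factors plus membership (5.0, 6.2). The documents give no factor prevalence, no effect of the factors on bleeding, no number of active sites, no biased-coin probability, no competing-event rate and no loss rate. The 5% inflation in 16.1 covers only ineligibility and cancellation. All of these are therefore assumptions below.

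**Step 1: the plan's own figure.** With the pooled rate 0.135, the null SE is √(2 × 0.135 × 0.865 / 176) = 0.03643. The alternative SE is √((0.09 × 0.91 + 0.18 × 0.82) / 176) = 0.03611.
- Two-sided 5%: (0.09 − 1.960 × 0.03643) / 0.03611 = 0.515, power 69.7%. This reproduces the stated 70%.
- One-sided 5%, as in 16.21: (0.09 − 1.645 × 0.03643) / 0.03611 = 0.833, power 79.8%.

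The conflict over sidedness between 16.1 and 16.21 is a separate matter. The one-sided test is taken here as 16.21 writes it.

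**Step 2: Z-test against CMH after minimisation.** 20,000 simulated trials per row, N = 352, biased coin 0.9, factor prevalences 0.6, 0.35 and 0.5, 20 sites. Risk is 13.5% in both arms for size, and 9% against 18% for power. CMH is stratified on the 8 cells of the three factors. Monte Carlo SE is about 0.15 points for size and 0.3 for power.

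| Assumed effect on bleeding | Size Z | Size CMH | Power Z | Power CMH |
|---|---|---|---|---|
| None | 4.9% | 4.9% | 80.2% | 79.8% |
| OR 1.5, all three | 5.0% | 5.2% | 80.6% | 80.6% |
| OR 2, all three | 4.7% | 4.9% | 80.8% | 81.5% |
| OR 3, all three | 4.3% | 5.1% | 81.1% | 83.0% |
| OR 3, one factor | 4.7% | 4.9% | 80.6% | 80.9% |

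The power gains are worth about 0, 6.5 and 21 patients in total at OR 1.5, 2 and 3 on all three factors. Each is twice the difference in per-arm n that gives the two simulated powers under the Step 1 formula.

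Two further simulations under other assumptions agree:
- N = 370, prevalences 0.75, 0.25 and 0.45, with site effects where the factors are prognostic: Z-test size was 5.1%, 4.6% and 4.3% with no, moderate and strong factor effects. CMH changed power by −0.2, +0.3 and +1.4 points.
- Prevalences 0.8, 0.15 and 0.5: power for Z against CMH was 80.0% vs 79.9% (OR 1.5), 80.7% vs 81.0% (OR 2) and 80.7% vs 82.2% (OR 3).

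**Step 3: variance of the cumulative incidence.** Let F₁ and F₂ be the cumulative incidences of the event and of the competing events, λ₁ and λ₂ their hazards, and Y(t) the probability of still being at risk and uncensored. The large-sample Aalen-Johansen variance at time T is

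(1/n) ∫₀ᵀ { [1 − F₂(t) − F₁(T)]² λ₁ + [F₁(T) − F₁(t)]² λ₂ } / Y(t) dt.

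Without censoring this equals F₁(1 − F₁)/n, the binomial form. A case by hand: F₁ = 0.135, no competing events, exponential loss with 10% probability by 12 months.
- λ₁ = −ln 0.865 = 0.1450 and g = −ln 0.9 = 0.1054.
- n × variance = 0.865² × (0.1450 / 0.2504) × (1/(0.865 × 0.9) − 1) = 0.1233. The binomial form gives 0.135 × 0.865 = 0.1168.
- SE ratio = √(0.1233 / 0.1168) = 1.028. The size of a nominal one-sided 5% test is 1 − Φ(1.645 / 1.028) = 5.5%.

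The full range takes F₁ = 9%, 13.5% and 18%, competing events of 20% or 40%, and exponential or uniform censoring. Size comes from 20,000 simulations per scenario, 176 per arm, 13.5% in both arms, with the censored share counted as observed.

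| Censored | True SE / binomial SE | Size, binomial variance |
|---|---|---|
| 0% | 1.00 | not inflated |
| 10% | 1.02–1.04 | 5.6–5.9% |
| 20% | 1.05–1.08 | 6.4–6.6% |
| 30% | 1.08–1.14 | 7.2–7.6% |

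With a delta-method variance, size was 5.0–5.3% throughout. If 30% is instead the underlying loss probability, before events remove some patients from risk, the formula gives a ratio of 1.09–1.10 and a size of 6.5–6.7%. The two sets of figures differ in how the censored share is counted; they agree in direction and scale.

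**The case against.** **The Z-test is prespecified, valid and of the same family as the sample-size calculation.** This stands. Stratifying is an improvement, not the correction of an error.

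**The gain may be nil.** This also stands. Appendix III presents the Khorana score as a predictor of VTE, and nothing in the documents shows that any of the three factors predicts bleeding. If none does, CMH costs about 0.4 points. The gain also shrinks with less even prevalences, to about 0.3 points at OR 2.

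**Eight cells of 44 on average can hide small ones.** True. Under the prevalences 0.6, 0.35 and 0.5, the smallest expected cell is 352 × 0.4 × 0.35 × 0.5 ≈ 25 patients. Under 0.8, 0.15 and 0.5 it is 352 × 0.2 × 0.15 × 0.5 ≈ 5. CMH size nevertheless stayed acceptable.

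**Section 16.21 gives no variance formula or denominator.** This is the best objection to the second point. The sponsor may intend a normal approximation around the cumulative-incidence estimate with a suitable variance. A binomial variance is the natural reading of the words, but one clarifying sentence would settle it. The analyses concerned are also labelled as not part of the primary analysis.

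**The stratified Cox model already covers both points.** Only as support. It uses the factors and handles censoring, but it estimates a hazard ratio. It does not replace the 12-month risk-difference test or supply a variance for the incidence differences.

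**Conclusion.** Both points hold, and both are minor.

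The primary and six-month Z-tests remain valid after minimisation. In the main simulation their one-sided size was 4.3–5.0% against a nominal 5%. Stratifying on the three factors is worth between −0.4 and +1.9 points of power. The sign and size depend on how strongly the factors predict bleeding, which the documents do not show.

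The cumulative-incidence tests, read literally, are correct with no loss and become mildly anti-conservative as loss grows: about 5.6–5.9% at 10% censored and 7.2–7.6% at 30%. That conclusion rests on the literal reading of the test sentence and on assumed censoring and competing-event rates. It touches secondary analyses only.

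**What to change.** - **16.21 (primary) and 16.22 (six months):** use a CMH test stratified by the three Section 5.0 factors, one-sided 5% as now written, and report the Mantel-Haenszel risk difference with its confidence interval. Keep the unstratified Z-test as a sensitivity analysis.
- **Leave registering membership out of the strata.** With more than 80 centers in the consortium, crossing it with 8 cells could give over 600 cells (80 × 8 = 640) for 352 patients.
- **16.21 to 16.23, cumulative-incidence differences:** replace the binomial approximation with an Aalen or delta-method variance of the Aalen-Johansen estimator, and state the formula. If that is what the plan already intends, one clarifying sentence is enough.

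The cost is SAP wording and standard software. The factors are recorded at randomization, and no patients, visits or data are added. The downsides are an estimate pooled across strata and the loss of about 0.4 points of power if no factor predicts bleeding. The choice should be fixed before unblinding.
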